11.2.2 Serious adverse event

A serious adverse event is an AE occurring during any study phase (*eg*, run-in, treatment, washout, follow-up), and at any dose of the investigational product, comparator or placebo, that fulfills one or more of the following criteria:

- results in death
- is immediately life-threatening (defined as an immediate risk of death from the event as it occurred)
- requires in-patient hospitalization or prolongation of existing hospitalization (Exception: hospitalization for elective treatment of a pre-existing condition that did not worsen during the study is not considered an adverse event. NOTE: Complications that occur during hospitalization are adverse events and if a complication prolongs hospitalization, then the event is serious)
- results in persistent or significant disability or incapacity
- is a congenital abnormality or birth defect
- is an important medical event that may jeopardize the subject or may require medical intervention to prevent one of the outcomes listed above.
- Is a Grade 4 laboratory abnormality.

The causality of SAEs (their relationship to study treatment) will be assessed by the investigator(s).

11.3 Dosing Delays/Dose Modifications

Dose reductions are to be made according to the system showing the greatest degree of toxicity. Toxicities will be graded using the NCI Common Terminology Criteria for Adverse Events (CTCAE) Version 3.

Dose reductions for toxicity should be made according to guidelines, which follow. A maximum of two 50mg (bicalutamide) dose reductions will be allowed per patient.

11.3.1 Gastrointestinal Toxicity

If \geq grade 3 diarrhea occurs, that is not controlled with anti-diarrheal agents (eg. loperamide), bicalutamide should be withheld until resolution to \leq grade 1, then reinstituted at the next lower dose level.

11.3.2 Breast Pain/Tenderness

If \geq grade 3 breast pain occurs, that is not controlled with non-opioid pain medications (NSAIDs, Tylenol), bicalutamide should be withheld until resolution to \leq to grade 1, then reinstituted at the next lower dose level. If \geq grade 3 breast pain occurs at a reduced dose level, and is not controlled with non-opioid pain medications, bicalutamide should be withheld until resolution to \leq grade 1, then reinstituted at the next lower dose level. If, after 2 dose reductions (to 50mg PO daily), \geq grade 3 breast pain persists, opioid pain medicine is encouraged. If symptoms persist, patient may be referred to a radiation oncologist (if no breast irradiation to palliate symptoms. If none of these interventions successfully alleviates symptoms, and if \geq grade 3 breast pain persists, then patient will be discontinued from study. Toxicity will be reported, and patient will be evaluated as unable to tolerate bicalutamide. If \leq grade 2 breast pain persists, patient may elect to stop treatment on study, or to continue. If patient chooses to discontinue study treatment, toxicity will be noted; however, this will not constitute unacceptable toxicity for purposes of adverse event reporting.

11.3.3 Hot flashes

If \geq grade 3 hot flashes occur, bicalutamide may be reduced to the next lower dose level, at the discretion of the treating physician. Pharmacologic intervention with low-dose SSRI (or an alternative oral therapy that has been demonstrated to have beneficial effect for treatment of hot flashes greater than that reported for placebo eg. clonidine, buproprion) may be administered. If \geq grade 3 hot flashes persist at lower dose level, a second dose reduction may be instituted. If \geq Grade 3 hot flashes persist at lowest treatment dose (50mg), patient will be taken off study, and adverse effect will be reported as intolerable toxicity. If \leq grade 2 hot flashes persist at lowest treatment dose (50mg), patient grade 2 hot flashes persist at lowest treatment dose (50mg), patient for treating physician. Toxicity will be reported; however, it will not constitute unacceptable toxicity for purposes of adverse event reporting.

11.3.4 Abnormal Hepatic Function

Bicalutamide should only be administered if hepatic function is within the parameters established in the eligibility criteria. Hepatic toxicity from bicalutamide may occur but it is uncommon. Therefore, hepatic dysfunction that occurs while the patient is on study should prompt an evaluation to determine the cause, including the possibility of progressive metastatic disease and hepatotoxicity from concurrent medications. A maximum of 2 weeks will be permitted for liver enzymes to return to within normal range for the institution.

If transaminases (ALT/AST) are elevated > 2.5x normal levels, treatment should be withheld until levels fall to ≤ 2.5 x normal levels. If total bilirubin is elevated > 1.5 x normal level, treatment should be withheld until level falls to ≤ 1.5 x normal levels. If alkaline phosphatase is elevated > 2.5 x normal value, treatment should be withheld until levels fall to ≤ 2.5 x normal level (unless bone metastases are present in the absence of liver metastases). A dose reduction should then be administered following resolution of any or all of these liver enzyme abnormalities.

If transaminases are subsequently elevated > 2.5 x normal; or, if total bilirubin is elevated > 1.5 x normal value, or if alkaline phosphatase is elevated > 2.5 x normal value (unless bone metastases are present in the absence of liver metastases), treatment will again be withheld until AST/ALT decrease to \leq 2.5 x normal, total bilirubin decreases to \leq 1.5 x normal value and alkaline phosphatase decreases to \leq 2.5 x normal value. A second dose reduction should then be administered.

If, after 2 dose reductions, AST, ALT, total bilirubin and/or alkaline phosphatase remain elevated, patient should be taken off study, and laboratory abnormalities should be reported as an unacceptable toxicity.

[figure not shown]

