4.3 Intervention

Patients will receive bicalutamide at a dose of 150mg PO daily. Patients will be seen monthly for an assessment by a care provider familiar with the protocol. Clinical assessment and serum studies will be performed per protocol (See Time and Events Schedule, Section 10). Patients may be seen before their scheduled monthly follow-up if they are experiencing any adverse effects or symptoms that may be consistent with progression of disease. Patients will undergo a radiologic extent of disease evaluation (EOD) every 3 months. An EOD may be performed earlier than a 3 month interval if progression of disease is suspected. Response will be evaluated using RECIST criteria as complete response (CR), partial response (PR), stable disease (SD) or progressive disease (PD).

If a patient experiences unacceptable toxicity at the initial dose level, up to two dose reductions of 50mg each will be permitted. Dose reduction of bicalutamide from the initial dose of 150mg PO daily to100mg PO daily will occur for an individual patient if that patient experiences unacceptable toxicity. A second dose reduction of 50mg is acceptable. Toxicities will be graded using the NCI Common Terminology Criteria for Adverse Events (CTCAE) Version 3. Treatment may be delayed no more than 2 weeks to allow recovery from acute toxicity. In the event of a treatment delay exceeding 2 weeks, the patient will be withdrawn from the study.

[figure not shown]
A patient will be withdrawn from the study in the following situations:

- For an unacceptable toxicity, defined as a Grade 3 or 4 non-hematologic toxicity after 2 (50 mg) dose reductions (see Section 11.2.5); or
- For unacceptable toxicity that fails to resolve after a maximum treatment delay of 2 weeks; or
- Progression of disease

Treatment with bicalutamide will continue until one or more of the criteria for withdrawal from study are met. After 6 months of treatment, patients will be considered responders if they achieve a CR, PR or SD by RECIST criteria. At the investigator's discretion, and in the absence of disease progression by RECIST criteria, treatment with bicalutamide may continue beyond 6 months. Study drug is provided by AstraZeneca.

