11.1 TOXICITIES/SIDE EFFECTS

These adverse event management guidelines are intended to ensure the safety of each patient while attempting to characterize the safety and tolerability of the test products. In agreeing to the provisions of this protocol, the investigator accepts all legal responsibilities for prompt notification of SAEs to the SAE manager in the Office of Clinical Research and to AstraZeneca as per section 11.4.

Adverse events occurring during the study will be graded according to the NCI CTCAE Scale Version 3.0 (see http://ctep.cancer.gov/forms/CTCAEv3.pdf) where applicable. Adverse events that are not included on the toxicity scale will be designated as Grade 1 = mild, Grade 2 = moderate, Grade 3 = severe, Grade 4 = life-threatening, and Grade 5 = death.

The investigator should evaluate all adverse events and should make an immediate effort to determine their etiology. Adverse events that are determined not to be possibly, probably, or definitely related to study drug may not require further evaluation but will need to be recorded on the CRFs. Study medication may be interrupted for an adverse event at the discretion of the investigator. Patients requiring toxicity management should be assessed and evaluated at least weekly as indicated by the severity of the event.

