13.0 CRITERIA FOR REMOVAL FROM STUDY

Patients will be removed from the study if any of the following conditions apply:

- intercurrent illness which would in the judgment of the investigator effect assessments of clinical status to a significant degree or require discontinuation of drug;
- unacceptable toxicity;
- progressive disease;
- request by the patient to withdraw;
- patient non-compliance with protocol;
- irradiation of an indicator lesion during the trial;
- if at the discretion of the investigator continued treatment would be harmful or ineffective.

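### Section 11.3.4 points a patient with drug-related or unexplained jaundice that recovers within 2 weeks to restart, up to twice, although the attached insert says to stop the drug for jaundice

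*Combined protocol and SAP*

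**What the plan says.** Section 11.3.4 sets hold limits of 2.5 x normal for ALT/AST and 1.5 x normal for bilirubin. For bilirubin it reads: "If total bilirubin is elevated > 1.5 x normal level, treatment should be withheld until level falls". After recovery: "A dose reduction should then be administered following resolution of any or all of these liver enzyme abnormalities". If the values rise above the limits again, the hold is repeated, and then: "A second dose reduction should then be administered". The dose table in 11.3.5 makes the two restart doses 100 mg and 50 mg.

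Two other parts of the section bear on this. It asks for a work-up, in that "hepatic dysfunction that occurs while the patient is on study should prompt an evaluation to determine the cause". It also sets a time limit: "A maximum of 2 weeks will be permitted for liver enzymes to return to within normal range for the institution". Section 4.3 adds the consequence: "In the event of a treatment delay exceeding 2 weeks, the patient will be withdrawn from the study".

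The Warnings (Hepatitis) part of the insert in Appendix A says to stop the drug at once, and follow liver function closely, if the patient becomes jaundiced at any time or if ALT exceeds twice the upper limit of normal. The insert is silent on whether the drug may be restarted after recovery.

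**The concern.** The hepatic rule asks how high the value went and whether it came back in time. It does not ask why it rose. Once the hold ends, jaundice that the work-up attributes to bicalutamide, or cannot explain, gets the same instruction as a brief mild rise. For jaundice the insert says stop, the protocol says hold and then restart, and 11.3.4 does not say why it differs.

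The wording is also firmer here than next door. Section 11.3.5 makes reinstitution after other grade 3 or higher toxicities depend on medical judgement, and 11.3.3 leaves dose reduction for hot flashes to the treating physician. The hepatic rule has no such qualifier, although it governs the toxicity for which the insert reports rare deaths and hospitalisations, mostly in the first three to four months and so inside the 6-month assessment window. Section 5.1 states that the drug is untested in women at these doses. What is at stake is the safety of a small number of patients.

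**Working it through.** The plan gives no figure of its own on this point. Its design figures in 14.0 reproduce (28 patients, success at 4 or more, 5% against 20%: exact type I error 0.0491 and type II error 0.1602, stated as 5% and 16%) and are not touched.

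**1. The rules side by side**

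| Situation | Section 11.3.4 with 4.3 | Insert, Appendix A |
|---|---|---|
| Jaundice, bilirubin > 1.5 x, recovers within 2 weeks | Hold, restart at 100 mg; on recurrence hold, restart at 50 mg | Stop at once; silent on restart |
| Same, recovery slower than 2 weeks | Withdrawn | Stop at once |
| Cause found to be bicalutamide | No change to the restart instruction | Stop at once |

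The rules part company only where recovery is timely. The labelled dose in the insert is 50 mg with an LHRH analogue in men. The restart doses are 100/50 = 2 times and 50/50 = 1 times that dose, so neither is below it.

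**2. What the 2-week limit screens out.** It selects by speed of recovery. Assume that bilirubin halves every h days after the hold, with h from 7 to 14; this range is not in the documents. The highest peak that passes by day 14 is target x 2^(14/h). Section 11.3.4 names two targets, the hold limit and the institution's normal range, so both are shown.

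| h (days) | Target 1.5 x ULN | Target 1.0 x ULN |
|---|---|---|
| 7 | 1.5 x 2^2 = 6.0 | 1.0 x 2^2 = 4.0 |
| 10 | 1.5 x 2^1.4 = 3.96 | 1.0 x 2^1.4 = 2.64 |
| 14 | 1.5 x 2^1 = 3.0 | 1.0 x 2^1 = 2.0 |

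Under either target, values clearly above the 1.5 x hold limit can pass.

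**3. How often.** The insert puts hepatitis or marked enzyme rises leading to discontinuation at about 1%. As an upper guide, P(at least 1 of 28) = 1 - 0.99^28 = 0.245, with 28 x 0.01 = 0.28 cases expected. Only a share of these would be jaundice or combined elevation recovering in time. That share is assumed:

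- 10% (p = 0.001): 1 - 0.999^28 = 0.028
- 25% (p = 0.0025): 1 - 0.9975^28 = 0.068
- 50% (p = 0.005): 1 - 0.995^28 = 0.131

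**The case against.** The strongest reply is that 11.3.4 is not the whole protocol. Section 11.1 says "Study medication may be interrupted for an adverse event at the discretion of the investigator", calls for a prompt search for the cause, and expects patients under toxicity management to be seen at least weekly according to severity. Section 13.0 lists, among conditions for which patients will be removed, "if at the discretion of the investigator continued treatment would be harmful or ineffective". An investigator who attributes jaundice to bicalutamide therefore has a direct route to removal, with the insert's warning in the same document. Progression removes the patient, grade 4 laboratory values and hospitalisations are reported as serious events (11.2.2), and the institutional committee monitors safety (16.1.3). This stands as a limit on size. It does not remove the gap, because it relies on each site overriding the one liver-specific instruction it has been given.

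A second reply is that the warning is used selectively, since the same sentence of the insert also stops the drug at ALT above 2 x. A reader might infer that the protocol's 2.5 x limit is therefore wrong. That does not follow: the entry criterion (6.2) and the hold limit agree at 2.5 x, so the protocol has an ALT rule of its own and applies it consistently. For jaundice it has no rule beyond the bilirubin hold.

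A third reply is that the size rests on assumptions, which is true. The halving model also ignores drug still in the body. With a half-life of 5.8 days, 2^(-14/5.8) = 19% remains at day 14; with the 10.4 days reported in severe liver disease, 2^(-14/10.4) = 39% remains. Jaundice may therefore clear more slowly than modelled, and the time limit would catch more cases. The same persistence makes a re-exposure slow to undo.

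**Conclusion.** The point holds in a narrow form and is worth fixing. For jaundice that is drug-related or unexplained and recovers in time, the specific instruction leads to as many as two re-exposures, against the attached warning and without a stated reason. The second needs recovery, recurrence and recovery again.

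A reader might infer more, namely that the protocol restarts after any liver abnormality whatever its severity or cause. The documents do not say that. Only values above the hold limits trigger the rule, slower recovery ends treatment, progression removes the patient, and 13.0 removes those for whom treatment is judged harmful. Nor does the insert forbid restart in so many words; it says stop. The 25% figure is the chance of any hepatic discontinuation event at the insert's rate, not of this one.

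The 3% to 13% range is illustrative. It rests on a rate from trials of the drug in prostate cancer and on an assumed share of 10% to 50%. The conclusion rests on the text and not on that range. The present rule affects neither the response endpoint nor its error rates, and no effect on the tolerability measure is claimed.

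**What to change.** Add to 11.3.4:

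> *Discontinue bicalutamide permanently for clinical jaundice unless the required work-up documents a cause other than bicalutamide. For other hepatic elevations, including combined bilirubin and transaminase elevation, restart at the next lower dose only if medically appropriate after the work-up, and not if the elevation is attributed to bicalutamide and bilirubin and ALT/AST have both risen from baseline above the hold limits.*

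Leave the entry and hold limits unchanged. A simpler rule that stopped the drug for every combined elevation above those limits would go too far. Section 6.2 admits patients with ALT/AST up to 2.5 x and bilirubin up to 1.5 x, so someone enrolled near both could be stopped for good after a trivial joint rise. Requiring attribution to bicalutamide protects that patient.

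The cost is two sentences in an amendment. No new tests are needed: ALT, AST and bilirubin are already measured every 4 weeks (10.0) and the work-up is already required. The downside is that an occasional patient with unexplained, reversible jaundice, or with a combined elevation attributed to the drug, loses the option of restart and counts as not tolerating treatment in the 6-month measure in 14.0.

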6.1 CRITERIA FOR SUBJECT ELIGIBILITY

6.2 Subject Inclusion Criteria

A patient will be eligible for androgen receptor expression testing if the following criteria are met:

- Pathologically confirmed adenocarcinoma of the breast which is ER(-) and PR(-).
- Non-measurable or Measurable, metastatic disease

IRB#: 07-022A(13)

A patient will be eligible for participation in the therapeutic trial if the following criteria are met:

- Androgen receptor expression testing confirms that the patient's tumor is ER(-)/PR(-) /AR(+). ER, PR and AR are considered positive if greater than 10% of cell nuclei are immunoreactive. Receptor testing may be performed on either primary tumor specimen or tissue from a metastatic site.
- Prior neo-adjuvant or adjuvant chemotherapy is allowed. Any number of chemotherapy regimens are allowed for metastatic disease. There is no restriction on prior treatment with hormonal agents.
- Prior treatment with trastuzumab must have been given if patient has Her2/neu positive disease (defined as IHC=3+ or FISH amplified).
- At least 2 weeks since prior cytotoxic chemotherapy. Patients should have recovered from all acute effects of such therapy.
- Absence of active brain metastatic disease or leptomeningeal disease. If patient has a history of brain metastases, lesions must be stable for at least 3 months (as documented by either head CT or brain MRI).
- At least 4 weeks from major surgery with full recovery
- ECOG performance status 0-1
- Age 18 years or greater
- Laboratory parameters as follows:
 - \circ ANC $\geq 1.5 \times 10^9$ cells/L
 - \circ Platelets $\geq 100 \text{ x } 10^9 \text{ cells/L}$
 - $\circ \quad Hgb \geq 9g/dL$
 - AST (SGOT), ALT (SGPT) ≤ 2.5 x upper limit of normal range (ULN); total bilirubin ≤ 1.5 x ULN; alkaline phosphatase ≤ 2.5 x ULN (unless bone metastases are present in the absence of liver metastases), creatinine ≤ 1.5 mg/dL
- If female of childbearing potential, pregnancy test is negative
- If fertile, the patient agrees to use an effective method to avoid pregnancy for the duration of the study
- Informed consent has been obtained

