11.2.1 Adverse event

An adverse event is the development of an undesirable medical condition or the deterioration of a pre-existing medical condition following or during exposure to a pharmaceutical product, whether or not considered causally related to the product. An undesirable medical condition can be symptoms (*eg*, nausea, chest pain), signs (*eg*, tachycardia, enlarged liver) or the abnormal results of an investigation (*eg*, laboratory findings, electrocardiogram). In clinical studies, an AE can include an undesirable medical condition occurring at any time, including run-in or washout periods, even if no study treatment has been administered. In cancer clinical trials, many AEs are in fact related to progression of the patient's underlying malignancy.

An adverse event includes:

- An exacerbation of a pre-existing illness;
- An increase in frequency or intensity of a pre-existing episodic event or condition;
- A condition detected or diagnosed after study drug administration even though it may have been present prior to the start of the study;
- Continuously persistent disease or symptoms that were present at baseline and worsen following the start of the study.

IRB#: 07-022A(13)

An adverse event does not include:

- Medical or surgical procedures (eg, surgery, endoscopy, tooth extraction, or transfusion); however, the condition that leads to the procedure is an adverse event (Procedures that occur during the trial should be recorded on the Concurrent Procedure CRF);
- Pre-existing diseases, conditions or laboratory abnormalities present or detected at the start of the study that do not worsen;
- Hospitalizations or procedures that are done for elective purposes not related to an untoward medical occurrence (eg, hospitalizations for cosmetic or elective surgery or social/convenience admissions);
- The disease being studied or signs/symptoms associated with the disease unless more severe than expected for the patient's condition;
- Overdose of study drug without any clinical signs or symptoms.

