11.3.5 Other toxicities

If toxicities are \leq grade 2, manage symptomatically if possible and retreat without dose reduction.

If toxicities are \geq grade 3, except for anemia, treatment should be withheld until resolution to \leq grade 1 or baseline if baseline was greater than grade 1, then reinstituted, if medically appropriate, at the next lower dose level.

For any grade 3 or 4 toxicity not mentioned above, treatment should be withheld until the patient recovers completely or to grade 1 toxicity. The treatment should then be resumed at the next dose level. For grade 1 or 2 toxicities, no dose reduction should be made.

A maximum of two weeks will be permitted for resolution of grade 3 or 4 toxicities. If toxicity has not resolved by the end of two weeks, patient will be taken off study.

IRB#: 07-022A(13)

Dose Modification Table

Dose Level	Bicalutamide (mg)	
(starting dose)		
0	150	
-1	100	
-2	50	

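### Section 11.3.4 drops the bone-metastasis waiver for alkaline phosphatase at the second-hold release and in the final off-study rule

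*Combined protocol and SAP*

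**What the plan says.** Section 6.2 caps ALP at 2.5 x the upper limit of normal at entry, "unless bone metastases are present in the absence of liver metastases". Section 11.3.4 opens by tying dosing to those same limits: "Bicalutamide should only be administered if hepatic function is within the parameters established in the eligibility criteria". It then sets out a sequence of steps:

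- **First hold and release.** Treatment stops if AST/ALT or ALP exceeds 2.5 x normal, or bilirubin exceeds 1.5 x normal, and resumes one dose level lower once they fall back. The ALP condition carries the waiver.
- **Second-hold trigger.** Same limits; the ALP condition carries the waiver.
- **Second-hold release.** AST/ALT, bilirubin and ALP must all be back within limits. The ALP part ("1.5 x normal value and alkaline phosphatase decreases to" 2.5 x normal or less) has no waiver.
- **Final rule.** "If, after 2 dose reductions, AST, ALT, total bilirubin and/or alkaline phosphatase remain elevated, patient should be taken off study", with the abnormality reported as an unacceptable toxicity. There is no waiver and no multiple of normal.

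Section 4.3 sets the consequence of a hold that cannot be released: "In the event of a treatment delay exceeding 2 weeks, the patient will be withdrawn from the study". Its list of withdrawal reasons includes unacceptable toxicity that has not resolved within that delay.

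**The concern.** The protocol accepts a raised ALP as compatible with treatment when it can be put down to bone disease. It says so at entry, at the first hold and at the second-hold trigger. At the last two steps the same value can keep a patient off drug or end her participation.

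Three things are at stake: the patient's treatment, the reason recorded for stopping it, and the tolerability endpoint in Section 14.0 (the percentage able to stay on daily drug for 6 months after at most two reductions). This is also a multicenter trial. One site could follow the opening sentence of Section 11.3.4 and keep such a patient on drug, while another follows the step rule and withdraws her.

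**Working it through.** **1. Does the text lead to withdrawal?** Take a patient with bone-only disease and ALP stable at 4 x normal (an illustrative value).

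- Entry: accepted under the waiver.
- Her ALP alone triggers neither hold, because both triggers waive it.
- First hold, for ALT above 2.5 x normal: ALT recovers, the ALP condition is waived, and she resumes at 100 mg.
- Second hold, again for ALT: ALT recovers, but release also requires ALP at or below 2.5 x normal. Hers stays at 4 x, so the condition is never met.
- After two weeks, Section 4.3 withdraws her, under its unresolved-toxicity reason.

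A second route needs a stricter reading. A waived patient has had two dose reductions, possibly for another toxicity, and the final rule is applied to an ALP that is still above normal.

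Both routes need more than a raised ALP. The first needs a second AST/ALT or bilirubin hold with ALP above 2.5 x normal. The second needs two completed reductions.

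**2. The plan's own figures.** Section 14.0: n = 28, success if 4 or more respond, 5% versus 20%. Exact binomial:

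- Type I error = P(X >= 4 | 28, 0.05) = 0.0491 (stated 5%).
- Power = P(X >= 4 | 28, 0.20) = 0.8398, so type II error = 0.1602 (stated 16%).

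These reproduce, and neither depends on Section 11.3.4.

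**3. How many patients?** The documents give no rate of holds at these limits and no share of waived patients. I assume a waived share of 10-30%, independent of liver events, and use three liver-event rates, all in men:

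- about 1%: hepatitis or marked enzyme increases leading to discontinuation (Appendix A);
- 3.1%: abnormal liver tests at 150 mg (Section 3.2);
- 7%: increased liver enzymes at 50 mg plus an LHRH analogue (Appendix A).

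Expected number of waived patients with at least one such event = 28 x rate x share:

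| Rate | 28 x rate | Share 10% | Share 30% |
|---|---|---|---|
| 1% | 0.28 | 0.028 | 0.084 |
| 3.1% | 0.868 | 0.087 | 0.260 |
| 7% | 1.96 | 0.196 | 0.588 |

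With a 40% share and the 7% rate the figure is 28 x 0.07 x 0.40 = 0.78. It passes one only with a rate about twice the highest in the documents: 28 x 0.15 x 0.40 = 1.68. Every figure counts a single event. The first route needs a second hold and an ALP above 2.5 x normal, so the number is smaller. The second route, through reductions for other toxicities, cannot be estimated from the documents.

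**4. What would one case cost?** On tolerability, a removal before 6 months costs 1/28 = 3.6 percentage points. At the 1% rate the expected cost is 0.028/28 = 0.1 to 0.084/28 = 0.3 points. If one patient were removed early and counted as a non-responder, power at 20% would be P(X >= 4 | 27, 0.20) = 0.818 instead of 0.840. That is conditional on a case occurring.

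**The case against.** The best case against is that the intent is clear. The opening sentence of Section 11.3.4 imports the eligibility limits, waiver included. The second-hold release stands in the same sentence as a trigger that carries the waiver, so reading one to mirror the other is natural. Section 4.3 allows delays for recovery from acute toxicity, which a stable bone-derived ALP is not. The final rule closes a hepatic sequence, so applying it after reductions for breast pain, say, is strained. Section 16.2.2 also lets a site seek prior IRB approval to alter a participant's plan.

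This shows what was probably meant, but the step rules still say something else, and a site following them would not be misreading them. The strained final-rule route is why I treat it as secondary.

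One could also defend a stricter end rule as liver safety in women never treated at this dose. That is hard to square with a protocol that waives ALP at both hold triggers. It does argue for limiting the final waiver to ALP that has not worsened.

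Section 11.3.5 gives limited support. It accepts recovery to "grade 1 or baseline if baseline was greater than grade 1" in one paragraph, but a later paragraph asks for complete recovery or grade 1 with no baseline alternative.

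A reader might infer four stronger things that the documents do not support:

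- *A stable raised ALP by itself leads to a hold.* It does not; both triggers waive it.
- *Several patients would be lost.* The working gives well below one of 28.
- *The two-week sentence is a third omission.* It reads "A maximum of 2 weeks will be permitted for liver enzymes to return to within normal range for the institution", but it follows text on dysfunction arising on study. Its mismatch with the 2.5 x and 1.5 x release limits affects every patient and every liver test, so it is not an error about bone metastases.
- *The adverse-event tables would be inflated.* Section 11.2.1 excludes "Pre-existing diseases, conditions or laboratory abnormalities present or detected at the start of the study that do not worsen". Section 17.2.1 records clinically significant baseline values as pre-treatment signs, and Section 17.2.5 analyses only events that begin or worsen on drug.

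**Conclusion.** The point stands as a minor wording fault with a real consequence. Section 11.3.4 omits the ALP waiver from the second-hold release and from the final off-study rule, and the final rule has no ALP threshold. Followed as written with Section 4.3, a waived patient whose ALT or bilirubin has recovered from a second hold would be withdrawn, with an unacceptable-toxicity label, for an ALP that eligibility accepts.

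Fewer than one of 28 patients is expected to be affected, probably far fewer. This rests on an assumed 10-30% waived share, independence, and liver-event rates in men. Sample size, decision rule and error rates are unchanged. I am confident about the omission itself, and less so about how often sites would apply the literal reading.

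**What to change.** Make two edits to Section 11.3.4 at the next amendment:

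1. In the second-hold release, add after the ALP condition: ("unless bone metastases are present in the absence of liver metastases").
2. In the final off-study sentence, state the ALP limit as more than 2.5 x normal, with the same waiver for ALP that has not worsened from baseline. Say how worsening is judged; the CTCAE version 3 grade, already used throughout, would serve.

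Leave the AST, ALT and bilirubin limits and the two-week sentence as they are. Whether to bring the ALT limits closer to the label warning in Appendix A is a separate safety decision for the sponsor.

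The cost is a few words. ALP is already measured at baseline and every cycle, so no data or visits are added. The small downside is that ALP does less liver-safety stopping in waived patients, in whom the AST, ALT and bilirubin rules still apply.
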